### **5.1.2 Study Subject Numbering**

Sites participating in the SUCCESS Study will each be assigned a site number prior to enrolling Subjects. Each enrolled Subject will be assigned a Subject number. Site study staff will use the electronic case report form (eCRF) assigned Subject number to complete documentation of the screening/enrolment log following appropriate consenting. Subject study identification numbers will consist of the aggregate of site number followed by a sequential number, where “01” is the first enrolled Subject as the corresponding site.

### **5.1.3 Subject Terminations**

Subjects will be considered discontinued from the study if any of the following occur:

1. Subject voluntarily withdraws from the study. Participation in the SUCCESS Study is voluntary. Subjects may withdraw consent at any time by completing an informed withdrawal form. Reasonable attempts will be made to determine the reason for withdrawal of consent. Data obtained prior to withdrawal enrolled will be included in endpoint data analysis, but no data will be obtained subsequent to withdrawal.
2. Investigator withdraws Subject from the study due to safety concerns. If, during the conduct of research, an Investigator determines that participation in the study may increase the hazard to a subject that is not acceptable, an Investigator may withdraw the Subject from the study due to safety concerns.
3. Lost to Follow Up: In the event that a Subject fails to return for the 30 days and/ or 6 months follow-up visits and is unable to be reached at the Subject's last known telephone number, a certified letter will be sent to the Subject's last known mailing address to remind the Subject of study obligations. Once all reasonable attempts to contact the Subject have been made, including contacting through the Subject's general practitioner, the Subject is considered lost to follow-up. Each attempt to contact a Subject will be documented.

If, during the conduct of the study, a Subject dies, all available information related to the event should be obtained. Within 24 hours from study staff becoming aware of the event, an appointed Rapid Medical representative/study monitor should be notified by completing the appropriate study termination forms in the Subject's eCRF.

Maximal completeness of the CRF for subject that died should be attempted and ensured by the following:

- If death occurs while the Subject is in the hospital, a copy of the death summary report should be submitted. In case of an autopsy, a copy of the autopsy report should also be submitted.
- If death occurs outside the hospital setting, effort should be made to obtain all information related to the death along with an Investigator's summary of the events associated with the death.

## **5.2 Site Selection, Training and Initiation**

### **5.2.1 Selection**

Sites will be selected by their ability to provide complete data sets with robust analyses for all safety and effectiveness outcomes with minimal risk to the subjects (i.e. CT up to 24h post procedure and 6 months angio to determine Raymond Scale score).

### **5.2.2 Training**

Investigators and Site Personnel will be trained on the surveillance plan prior to site initiation of enrollment. Training will be documented on the Training Log and cover the following topics:

1. Study objectives
2. Surveillance plan review
3. Delegation of authority
4. Process for Informed Consent as well as IRB requirements
5. Electronic case report form use and completion guidelines
6. Enrolment procedures
7. Protocol Deviation documentation
8. AE and SAE event reporting
9. Device malfunction reporting
10. Comaneci Instructions for Use
11. Device traceability
12. Image collection and core lab submission
13. Investigator responsibilities and obligations
14. General Good Clinical Practice (GCP) guidelines
15. Regulatory requirements including essential documents

Changes to existing SUCCESS Study staff responsibilities, as documented on the Delegation Log, or addition of new study personnel will require investigational plan training, as appropriate.

### **5.2.3 Initiation**

Rapid Medical, or a representative of Rapid Medical, will conduct study training as described in section 5.2.2.

Prior to actively recruiting/enrolling Subjects, Clinical sites must provide the following documentation to Rapid Medical:

1. IRB approval for the Surveillance Plan
2. IRB and sponsor approved Informed Consent Form for the study
3. Investigator(s') *curriculum vitae* (CV)
4. Financial Disclosure(s) for the PI and Sub-I(s)
5. Signed Clinical Trial Agreement (CTA) including Confidentiality Agreement
6. Training Log documentation to verify the appropriate study staff has been trained on the protocol, device, eCRFs and study conduct.

Sites will be officially notified of site activation through receipt of an activation letter or email.

## **6. STUDY DESIGN**

The SUCCESS Study is a multi-center, prospective, postmarket safety surveillance study in up to 30 US centers. The Surveillance is to continue until complete data on the deployment of 90 devices with complete 30-day patient status are obtained in order to assess safety and performance as used in postmarket clinical practice in the U.S.

### **6.1 Study Duration**

All patients who are treated with the Comaneci device and consented to allow data collection will be followed for 180 ( $\pm 21$ ) days post-procedure.

### **6.2 Subject Inclusion/Exclusion Criteria**

Subjects are considered enrolled in the SUCCESS Study only after an attempt is made to introduce the Comaneci device through the arterial sheath and subject was properly consented.

#### **6.2.1 Inclusion Criteria**

In order to assure that the probable benefits outweigh the probable risks for the Comaneci Embolization Assist Device, as indicated in the IFU, the subjects must meet all of the following inclusion criteria:

1. Patient has a documented intracranial ruptured or unruptured aneurysm, suitable for embolization by coils.
2. Patient is considered for treatment with coil embolization assisted by the Comaneci Device for wide-necked intracranial aneurysms with neck width  $\leq 10$  mm. A wide-necked intracranial aneurysm is defined by the neck width as  $\geq 4$  mm or a dome-to-neck ratio  $< 2$ .
3. A signed informed consent by the patient or legally authorized representative.

#### **6.2.2 Exclusion Criteria**

Patient should be treated by the Comaneci device in accordance with the approved device label. (i.e. doesn't meet the contraindication criteria, as described in the IFU):

1. Patient with known hypersensitivity to nickel-titanium.

[figure not shown]
## **7. Data Collection**

All procedures will be according to the standard practice at each site and determined by the treating physician including 6 months follow up. Procedures such as routine hospital examinations, brain CT scan or MRI will be performed according to each site's standard management protocol and relevant data will be properly documented in the patient's medical records.

### **7.1 Study**

Study flow of Subjects through the SUCCESS Study is illustrated in Figure 3.

## SUCCESS Study

\*Subjects with ruptured aneurysms: Due to the emergent nature of acutely ruptured aneurysms, informed consent may be obtained from the point of arrival at the medical treatment facility up to 72 hours after the study procedure. Consent must be obtained before any data is captured in the eCRF

Figure 3: Study Flow

## 7.2 Screening and Baseline Visit

Any subject who is consented for endovascular treatment of an IA that may potentially require use of the Comaneci device at the participating centers in the study will be approached for consenting prior to device use, using separate consent for the subject's participation in and data collected to be included in the SUCCESS study.

Subjects with ruptured aneurysms: due to the emergent nature of acutely ruptured aneurysms, informed consent may be obtained from the point of arrival at the medical treatment facility up to 72 hours after the study procedure.

For all subjects, consent must be obtained before any data is captured in the eCRF.

To reduce selection bias, accounting for all unsealed Comaneci devices in each IA case that may potentially require use of the Comaneci device at a clinical site for the period of enrollment to the study will be provided. The accounts will not provide patient information but will provide some indication of the device disposition.

An electronic Screening & Enrollment Log will include all IA patients treated at each site whether or not they are included in the study. Screening against study inclusion/exclusion criteria will be completed to determine potential eligibility. For each patient considered but not treated with Comaneci, the reason for not attempting to use Comaneci will be indicated. In addition, for patients where Comaneci was introduced into the body but who were not enrolled for follow up and data collection, or who denied post procedure consenting, the reason will be indicated in the electronic Screening & Enrollment Log by the attending physician. Sites will maintain this electronic log for the duration of the recruitment period of the study.

### 7.2.1 Patient Details:

- Year of Birth
- Gender
- Date of Treatment

### 7.2.2 Medical History:

- Presence or absence of multiple intracranial aneurysms
- Smoking history
- Presence or history of hypertension
- History of prior rupture of an intracranial aneurysm
- Family history of intracranial aneurysm
- Vital Signs (Height, Weight, Blood Pressure, Heart Rate)
- Concomitant diseases
- Laboratory- Standard Biochemistry and CBC, PT, PTT, INR
- Prior/Concomitant Medications (Coagulation and Antiplatelet)

### **7.2.3 Pre- Treatment Data:**

- Aneurysm size and location
- Pre-procedure mRS score (modified Rankin Scale)-up to 24h prior to treatment.
- Pre symptoms mRS
- NIHSS
- Pre op antiplatelet and/or coagulation medications

NIHSS will be performed by certified Study personnel.

mRS will be assessed by an independent clinician who is not a member of the investigational team.

### **7.2.4 Screen Failures**

Subjects who were consented and not treated with the Comaneci device (device was not introduced to the body) due to not meeting the indication of the device, such as aneurysm size and anatomy, will be considered screen failures and will not be followed up, but the reason for not introducing the Comaneci will be documented. Screen failures will not be included in the primary safety endpoint analysis.

## **7.3 Procedure**

### **7.3.1 Angiography**

Intraprocedural diagnostic catheter angiography will be conducted prior to device deployment to determine location and aneurysm morphological features. Diagnostic angiograms will be obtained as per standard of care. A final post-procedure angiogram (full A-P lateral image) will be obtained once all treatments have concluded, including rescue therapy, if necessary. CT of up to 24h postprocedure if performed as a standard of care will be analyzed for safety parameters, such as hemorrhage.

Angiography at end of procedure and 6 months, will be analyzed to determine Raymonds scale at both time points and stability of Raymond Roy score. All images are to be de-identified and submitted to the core lab for review:

The University of California at Los Angeles with the following address:

Angiography and Noninvasive Imaging Core Lab  
[name], FAAN, FAHA, FANA  
UCLA Department of Neurology  
Neuroscience Research Building  
[name]  
[name]

Procedure will be handled as standard of care, according to Comaneci device IFU, appendix A.

### 7.3.2 Intraoperative Data

Intraoperative data will be collected as described below:

- Devices, Coils
- Medications
- Comaneci Performance (such as deployment/removal success, neck coverage)
- Total procedure time
- Total time Comaneci was inflated
- Raymond Scale at the end of procedure, using post procedure DSA
- Intra- Procedural Complications and AEs (including a determination of the severity, seriousness, and relationship to the device or procedure). These will specifically include vessel perforation or dissection, intracranial aneurysm rupture, stroke, hemorrhage, death, inability to deploy or remove the device, and coil entanglement.

### 7.4 24 Hour (-6/+12) Follow-up

24 hours (-6/+12 hours) from time of procedure

- Complications and any AE's (including a determination of the severity, seriousness, and relationship to the device or procedure). These will specifically include stroke, hemorrhage and death.
- Concomitant antiplatelet and/or anticoagulant medications
- mRS Score (if performed) mRS should be assessed by an independent clinician who is not a member of the investigational team.
- CT (if performed up to 24 hours post procedure as a standard of care)
- If subject discharged within 24 h- Discharge status (for example, by CMS Patient Discharge Status Code)

**Note:** CT images will be sent to the Imaging Core Lab for evaluation.

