**PROTOCOL SUMMARY**  
**Postmarket Surveillance Plan (PS190001)**  
**-SUCCESS Study-**

Title	SU ccess in C omaneci-assist C oils E mbolization S urveillance S tudy
Short title	SUCCESS Study
Sponsor	Rapid Medical
Coordinating Principal Investigators	[name], Baptist Neurological Institute, Baptist Health System Jacksonville, FL  Co-Investigator: [name], Jacobs School of Medicine and Biomedical Sciences, University at Buffalo, New York
Product	Comaneci Embolization Assist Device
Objective	The objective of the Postmarket Surveillance Plan is to assess safety and performance as used in postmarket clinical practice in the U.S.
Study Design	This study is a multicenter, single arm, open, prospective, postmarket safety surveillance in up to 30 US centers
Device Description and Intended Use	The Comaneci Embolization Assist Device is indicated for use in the neurovasculature as a temporary endovascular device used to assist in the coil embolization of wide-necked intracranial aneurysms with a neck width $\leq$ 10 mm. A wide-necked intracranial aneurysm (IA) defines the neck width as $\geq$ 4 mm or a dome-to-neck ratio $<$ 2.  The Comaneci is comprised of a collapsible, fully retrievable, fine wire construction mounted on a wire shaft that expands to comply with the vessel diameter. It is delivered through a neurovascular microcatheter. The Comaneci is provided with a 3.5 French (F) peelable loading sheath.
Endpoints	
Safety
 
 
Periprocedural events*: Rates of all adverse events occurring within 24 hours post-procedure and hospital discharge status.
 
All adverse events at discharge and up to 30 days post procedure.
 
Functional status at discharge and 30 days assessed using the modified Rankin Scale (mRS).
 
 
Secondary safety endpoint: evaluation of the extent of any relationship between adverse event rate to operator experience.
 
(* ) Including vessel perforation or dissection, intracranial aneurysm rupture, stroke, hemorrhage, death, inability to deploy or remove the device, and coil entanglement
 
Efficacy

SUCCESS Study

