Statistical Analysis	
The rates of all adverse events occurring within 24 hours post procedure, hospital discharge status and after discharge for all opened devices at each participating clinical site during the surveillance period will be summarized. The numbers of individual adverse events of each type and the per subject incidence rate for each type of adverse event will be determined and reported along with 90% two-sided exact binomial confidence intervals. Separate event counts and incidence rates with corresponding confidence intervals will be summarized for adverse events determined to be serious, device-related, serious and device-related, procedure-related, serious and procedure-related, and severe. Listings for all adverse events will be compiled that provide full descriptions of each adverse event including determination of the severity, seriousness, and relationship to the device or procedure. Discharge status will be described with counts and percentages.
 
Effectiveness at six months will be descriptively summarized in terms of the number and percentage of subjects achieving successful aneurysm occlusion measured by Raymond scale grade I and II and by clinical outcome as measured by mRS shift analysis comparing preprocedure mRS (up to 24 h prior to treatment) with 6 month mRS. In addition, tetrachotomized (0,1, 2, 3-6) mRS analysis will also be performed. mRS will also be evaluated at discharge and 30 days. Successful aneurysm occlusion will also be evaluated at the end of procedure. Stability of occlusion will be evaluated by comparing the two angiographic studies that are 6 months apart. The distribution of scores will be summarized by counts and percentages. If only three month Raymond scale value is available but not the six month, the three month value will be used in these analyses. Similarly, the last available earlier mRS values will be used if the six month value is not available.

-----------------------------	--

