## Schedule of Events

Elapsed time/Study procedures	Baseline/Procedure	24 hours (-6/+12)	Discharge if different than 24 hours (-6/+12)	30 ( $\pm 7$ ) days	180 ( $\pm 21$ ) days**
Informed Consent	X				
Demographics	X				
Medical History and Concomitant Medications	X				
Brain CT Scan	X	X*			
Vital Signs	X				
mRS score +	X		X	X	X
NIHSS	X			X	
Clinical Laboratory	X				
Raymond scale	X***				X***
Intraoperative data	X				
Prior/concomitant medications	X	X	X	X	X
Adverse Events	X	X	X	X	X

(\*) If performed as a standard of care any time up to 24 hours post procedure

(\*\*) Will be collected if performed also at 90 ( $\pm 14$ ) days as a standard of care.

(\*\*\*) Post-procedure and 6 months imaging should use Digital Subtraction Angiography (DSA) for Raymond scale assessments.

(+) If in-person visits are not possible, mRS assessments may be performed remotely by structured telephone interviews.

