### 3.1 Endpoints

#### Safety

- Periprocedural events\*: Rates of all adverse events occurring within 24 hours post-procedure and hospital discharge status.
- All adverse events at discharge and up to 30 days post procedure.
- Functional status at discharge and 30-days assessed using the modified Rankin Scale (mRS).

**Secondary safety endpoint:** evaluation of the extent of any relationship between adverse event rate to operator experience

(\* ) Including vessel perforation or dissection, intracranial aneurysm rupture, stroke, hemorrhage, death, inability to deploy or remove the device, and coil entanglement

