### 7.5 Discharge, if different than 24 hours (-6/+12 hours)

If Subject is discharged in a time that is different than the 24 hours (-6/+12 hours),

the following data will be collected:

- Discharge status (for example, by CMS Patient Discharge Status Code)
- mRS Score- should be assessed by an independent clinician who is not a member of the investigational team.
- Complications and any AE's (including a determination of the severity, seriousness, and relationship to the device or procedure). These will specifically include stroke, hemorrhage and death.

- Antiplatelet and/or anti-coagulant Medications, if was changed from previous visit

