**Table 2: Schedule of Events**

Elapsed time/Study procedures	Baseline/Procedure	24 hours (-6/+12)	Discharge if different than 24 hours (-6/+12)	30 ( $\pm 7$ ) days	180 ( $\pm 21$ ) days**
Informed Consent	X				
Demographics	X				
Medical History and Concomitant Medications	X				
Brain CT Scan	X	X *			
Vital Signs	X				
mRS score +	X		X	X	X
NIHSS	X			X	
Clinical Laboratory	X				
Raymond scale	X***				X***
Intraoperative data	X				
Prior/concomitant medications	X	X	X	X	X
Adverse Events	X	X	X	X	X

(\*) If performed as a standard of care any time up to 24 hours post procedure

(\*\*) Will be collected if performed also at 90 ( $\pm 14$ ) days as a standard of care.

(\*\*\*) Post-procedure and 6 months imaging should use Digital Subtraction Angiography (DSA) for Raymond scale assessments.

(+) If in-person visits are not possible, mRS assessments may be performed remotely by structured telephone interviews.

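### mRS at discharge is a safety endpoint for every subject, but no discharge mRS is required of subjects who go home 18 to 36 hours after the procedure

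*Combined protocol and SAP*

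**What the plan says.** The endpoint carries no restriction. Section 3.1 lists "Functional status at discharge and 30-days assessed using the modified Rankin Scale (mRS") under Safety, the protocol summary does the same, and the summary's statistical paragraph adds "mRS will also be evaluated at discharge and 30 days".

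Collection depends on when the subject leaves hospital:

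- **Section 7.5** asks for mRS without qualification, but the visit takes place only under this condition: "If Subject is discharged in a time that is different than the 24 hours (-6/+12 hours").
- **Section 7.4**, the 24-hour visit, lists "mRS Score (if performed"). Adverse events and medications are collected there without that qualifier.
- **Both schedule tables** (protocol summary and Table 2) mark mRS at baseline, at 30 days, at 180 days and in the column headed "Discharge if different than 24 hours (-6/+12"). The 24-hour mRS cell is blank.
- **Section 7.10** refers to Table 2 for timing, so it adds no further requirement.
- **Section 8.6** expects few missing safety data and imputes none. Its carry-forward rule covers only the six-month analysis.

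Discharge status has a similar wording problem. Section 7.4 collects it under the line "If subject discharged within 24 h- Discharge status", and section 7.5 collects it only outside the 24-hour window.

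**The concern.** The endpoint is defined for everyone, but the only unconditional discharge mRS belongs to a visit that some subjects never have. A site that works from its visit list and schedule can leave the endpoint blank with no prompt to complete it.

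The gap depends on discharge timing. The population mixes ruptured and unruptured aneurysms, and subjects who leave after about a day are plausibly the uncomplicated ones. That is an inference; the documents give no discharge times. If it is right, the missing scores are mostly good ones, and the reported discharge distribution looks worse than the cohort's. Section 8.6's expectation of little missing data also need not hold for this endpoint.

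The stake is the accuracy of one descriptive safety endpoint in a study meant to reduce uncertainty about the safety profile. The primary effectiveness test, the sample size of 90 and the scheduled 30-day and six-month mRS are not touched.

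**Working it through.** **Window.** Section 7.4 sets the visit at 24 h with -6/+12. Then 24 - 6 = 18 h and 24 + 12 = 36 h.

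**What is required, by time of discharge**

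| Discharge after procedure | Visit that applies | Discharge mRS | Discharge status, read literally |
|---|---|---|---|
| Before 18 h | 7.5 | Required | Required |
| 18 to 24 h | 7.4 | Only if performed | Required |
| After 24 h, up to 36 h | 7.4 | Only if performed | Neither section asks for it |
| After 36 h | 7.5 | Required | Required |

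**Illustration of the bias.** The number of subjects, 90, is from section 5.1.1. All other inputs are assumptions, because the documents do not give them:

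- *f*: share discharged at 18 to 36 h.
- *u*: uptake of the optional mRS in that group.
- Proportion with mRS 3-6: 5% of in-window discharges, 35% of all others.

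Formulas:

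- True proportion = 0.05*f* + 0.35(1 - *f*)
- Proportion in collected data = [0.05*fu* + 0.35(1 - *f*)] / [*fu* + 1 - *f*]
- Expected number assessed = 90(*fu* + 1 - *f*)

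Worked case, *f* = 0.5 and *u* = 0.5: true = 0.025 + 0.175 = 20.0%. Collected = (0.0125 + 0.175) / (0.25 + 0.5) = 0.1875 / 0.75 = 25.0%. Assessed = 90 × 0.75 = 67.5. Excess = 5.0 points.

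| *f* | True | Collected, *u* = 0 (assessed) | Collected, *u* = 0.5 (assessed) | Collected, *u* = 0.8 (assessed) | Excess in points, *u* = 0 / 0.5 / 0.8 |
|---|---|---|---|---|---|
| 0.1 | 32.0% | 35.0% (81) | 33.4% (85.5) | 32.6% (88.2) | 3.0 / 1.4 / 0.6 |
| 0.3 | 26.0% | 35.0% (63) | 29.7% (76.5) | 27.3% (84.6) | 9.0 / 3.7 / 1.3 |
| 0.5 | 20.0% | 35.0% (45) | 25.0% (67.5) | 21.7% (81) | 15.0 / 5.0 / 1.7 |
| 0.6 | 17.0% | 35.0% (36) | 22.1% (63) | 18.6% (79.2) | 18.0 / 5.1 / 1.6 |

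**Smaller contrast.** With 10% in-window and 20% otherwise, the excess for *f* = 0.3, 0.5 and 0.6 is 3.0, 5.0 and 6.0 points at *u* = 0, and 1.2, 1.7 and 1.7 points at *u* = 0.5.

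**No link between timing and outcome.** The excess is zero for every *f* and *u*; only the number assessed falls.

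**The case against.** The best defence is that the plan does state the requirement. The summary says without condition that mRS is evaluated at discharge, and the heading of the discharge column implies that the 24-hour visit doubles as the discharge visit when the two coincide. On that reading, the qualifier in 7.4 is meant for inpatients not yet discharged, and the defect is one missing clause. The reading is reasonable, but it is not written down, and the working parts of the plan (7.4 and both schedules) say otherwise. The general sentence confirms the contradiction; it does not remove it.

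Other points carry some weight:

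- **Consequence.** Discharge mRS has no hypothesis or decision rule. Section 8.1 names 30-day functional status as a focus, and section 8.3 specifies a distribution only for the 30-day score. Affected subjects still have adverse events collected at 24 h and mRS at 30 days. This limits the weight of the point.
- **Size.** The largest excess needs a 60% in-window share, zero uptake and a 30-point contrast together. At a 10% share it is 3 points or less.
- **Direction.** Subjects discharged before 18 h do have a required mRS and may be the mildest of all. The illustration pools them with long stays. Bias towards worse scores is probable, not certain.
- **Discharge status.** Under a heading that defines the visit as 24 hours (-6/+12), the line can be read as meaning that visit, and section 8.2 asks for discharge status without a time limit. This is a wording fault and adds little to the main point.

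**Conclusion.** The concern holds. Discharge mRS is a listed safety endpoint with no subset, yet it is optional for anyone discharged 18 to 36 h after the procedure, and nothing in the schedules, section 7.10 or section 8.6 closes the gap. This rests on the text alone.

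The size of any bias cannot be determined from the documents. With 30% to 60% of subjects in the window and the assumed 5% versus 35%, the proportion with mRS 3-6 is overstated by 9 to 18 points at zero uptake, about 4 to 5 at half uptake and 1 to 2 at 80%. It is smaller with a lower in-window share or a weaker contrast, and zero if timing and outcome are unlinked. Because the endpoint is descriptive, this is a correction that should be made, and it does not threaten the study's main conclusions.

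**What to change.** 1. In section 7.4, make the mRS entry conditional: required if the subject is discharged in this window, otherwise if performed.
2. In the same section, tie the discharge-status line to discharge in this window, so that 24 to 36 h is covered.
3. In both schedule tables, add an mRS mark in the 24-hour column with a matching footnote.
4. For subjects already enrolled without the score, report discharge mRS separately for discharges inside and outside 18 to 36 h, with the number assessed and missing in each group. This step needs no change at the sites.

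**Cost.** Two lines in 7.4, one cell and one footnote in each table, and site notification. Section 10.1 treats changes without IRB approval as deviations, so allow for IRB review and possibly a small eCRF change. The practical burden is having the trained independent rater available around a short-stay discharge. The schedule footnote already eases this: "If in-person visits are not possible, mRS assessments may be performed remotely by structured telephone interviews". The sample size does not change.
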